1. PURPOSE OF STUDY

Aim 1: To examine the feasibility of the home-based transcranial direct-current stimulation (tDCS) apparatus and protocol (as well as the home-based tDCS sham protocol) for future use as an adjunctive treatment to prevent suicidal ideation (SI) relapse in adult patients with mood or bipolar disorders after discharge from the Comprehensive Psychiatric Emergency Program (CPEP) or inpatient unit to which they were admitted with SI or attempt.

Hypothesis 1: We expect at least 70% of the subjects to complete at least 5 of recommended 10 RS-tDCS sessions within three weeks of receiving the home-based tDCS device.

Aim 2: To detect a preliminary signal of the effect of adjunctive home-based tDCS on indices of SI measured with The Columbia-Suicide Severity Rating Scale (C-SSRS) in adult patients with mood or bipolar disorders after discharge from the CPEP or inpatient unit of which they were admitted with SI or attempt.

Hypothesis 2: Subjects in the active tDCS arm will report less suicide ideation intensity (as measured by C-SSRS) than subjects in the control (sham) group at the end of treatment, which will help to determine an effect size for use in the sample size calculation for a full randomized controlled trial.

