4. STUDY DESIGN

This is a single-center, randomized, sham-controlled, double-blind clinical study to investigate the feasibility of delivering RS-tDCS sessions for high-risk patients for suicide in the days following discharge from the CPEP or inpatient unit which they were admitted with SI or attempt. We plan to assess up to 80 adult patients for eligibility over 12 months of which 20 will be enrolled and randomized. Clinical assessments will be performed at baseline, post-treatment day 14 (14 days after the first RS-tDCS session), and follow-up day 30 and 60 (30 and 60 days after the first RS-tDCS session, respectively).

All study outcome measures are described in Table 1.

Time points		in-person	remote	
	Measures		S1 to S10	C14, C30, and C60
Eligibility screening		Х		
Informed consent		Х		
Enrollment		Х		
		Baseline		
Demographic data		Х		
General medical history		X		
Orientation tDCS session		X		
Loan agreement		Х		
	Feasibility		X*	
	C-SSRS	X		Х
	RRS	X		Х
	CAST	Х		Х
	MADRS	Х		Х
	C-SSRS SV		X	
	Side effects questionnaire		X	
	Treatment emergent event review		Х	Х
	Acceptability questionnaire		X**	
	Blinding assessment		X**	

Table 1. Study's time points and measures.

C14, C30, and C60: clinical assessments at post-treatment day 14, follow-up day 30 and follow-up day 60; CAST: The Concise Associated Symptoms Tracking; C-SSRS: The Columbia-Suicide Severity Rating Scale; C-SSRS SV: The Columbia-Suicide Severity Rating Scale – screening version; MADRS: Montgomery-Asberg Depression Rating Scale; RRS: Ruminative Responses Scale; S1 to S10: remotely supervised transcranial direct current stimulation (RS-tDCS) sessions one to ten.

*Number of completed RS-tDCS sessions per participant within three weeks of the study.

**applied only once, after the final RS-tDCS session (the tenth session).

Primary outcome measures:

Page 5 of 22 Version Date: 10/09/2023 1. Feasibility of the intervention – number of completed remotely supervised transcranial direct current stimulation (RS-tDCS) sessions, for both active and sham groups:

We expect at least 70% of the subjects to complete at least 5 of recommended 10 RS-tDCS sessions within three weeks of receiving the home-based tDCS device.

This criterion is based on a study that reported dropout rates between 22% and 25% of homebased tDCS for patients with bipolar depression (40) and that therapeutic effects with tDCS could be achieved within one week of treatment (24).

Secondary outcome measures:

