Subjects will be randomized 1:1 to either active or sham RS-tDCS. The active RS-tDCS delivers a constant current intensity of 2mA on the subject's scalp, with SNAPstrap headgear and 5x7 (35cm2) SNAPpads positioning bilaterally (anodal-left and cathodal-right), on the DLPFC, for 30 minutes. A similar protocol's administration was found effective, safe, and tolerable as an add-on intervention to decrease depressive symptoms in patients with bipolar depression (45). Sham tDCS looks identical to a typical RS-tDCS cap but delivers a 30-second ramp-up (0-2 mA) stimulation followed by a 30-second rampdown (2-0 mA) at the beginning and end of the application. Figure 2 shows a representation of the electric current delivered by the active and sham RS-tDCS.

[figure not shown]

Figure 2. Stimulation protocol. Active tDCS (upper) and sham tDCS (lower).

The tolerability and safety of home-based tDCS were assessed over 6,779 sessions from six clinical trials. Sessions were administered daily, with treatment ranging from 10 to 60 sessions per subject. The authors reported no serious adverse events, a similar proportion of tingling (68%), itching (41%), and warmth sensation (42%) between active and sham groups, and no participant discontinuation due to lack of tolerability (39).

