17. DATA ANALYSIS PLAN

To assess feasibility, the primary outcome of this study, we chose a sample size of 20. To infer feasibility, at least 50% of the sessions should be performed successfully per subject for at least 70% of the subjects. This criterion is based on a study that reported dropout rates between 22% and 25% of home-based tDCS for patients with bipolar depression (40) and that therapeutic effects with tDCS could be achieved within one week of treatment (24). For each time point established, we will compare groups with a t-test or chi-square test, for continuous and categorical data, respectively (a p value<0.05 will be considered significant).

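### About 10 subjects per arm cannot supply the effect size for the full trial, and section 17 applies p<0.05 to some 15 unadjusted comparisons without calling them exploratory

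*Combined protocol and SAP*

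**What the plan says.** Section 1 (Purpose of Study) makes feasibility Aim 1. Aim 2 looks for a preliminary signal on suicidal ideation. Hypothesis 2 predicts lower end-of-treatment C-SSRS intensity in the active arm, and describes this result as one "which will help to determine an effect size for use in the sample size calculation for a full randomized controlled trial".

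Section 17 (Data Analysis Plan) ties the sample size to feasibility alone: "To assess feasibility, the primary outcome of this study, we chose a sample size of 20". The success rule is that "at least 50% of the sessions should be performed successfully per subject for at least 70% of the subjects". No target effect, SD, power or precision is given. Section 4 (Study Design) sets the allocation: "Subjects will be randomized 1:1 to either active or sham RS-tDCS".

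On efficacy, section 17 has one sentence: "For each time point established, we will compare groups with a t-test or chi-square test", with the rule that "a p value<0.05 will be considered significant". It does not single out the Hypothesis 2 comparison, label any test exploratory, address multiplicity or mention confidence intervals.

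Section 4 lists five clinical outcomes measured at days 14, 30 and 60: C-SSRS intensity, the proportion answering no to C-SSRS questions 1 and 2, RRS, CAST and MADRS. Section 5 admits only subjects without current ideation, so C-SSRS intensity starts at or near its floor.

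**The concern.** The plan asks two things of the efficacy data that 20 subjects cannot give.

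The first is an effect size on which to build a larger trial. An estimate from 10 per arm is dominated by sampling error, and required sample size varies with the inverse square of the effect, so that error is magnified. A trial planned on a chance overestimate would be too small to detect the real effect.

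The second is a set of significance verdicts. With a 0.05 threshold at every outcome and visit and no ranking among them, an isolated significant result could be read as the preliminary signal of Aim 2, although Hypothesis 2 concerns one outcome at one time.

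**Working it through.** **Inputs.** From the documents: 20 subjects, 1:1, so n = 10 per arm; threshold 0.05; five outcomes; three visits. Assumed, because the documents are silent: two-sided tests, 80% power for the full trial, true d of 0.3, 0.5 or 0.8, and the correlations in step 4.

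**1. The plan's own figure.** The 20 cannot be re-derived, since no formula or target is given. The feasibility threshold is 0.70 × 20 = 14 subjects; 14/20 has an exact 95% interval of 46% to 88%.

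**2. Precision of the pilot effect.** The observed d equals t/√(n/2), where t is noncentral with 2n − 2 = 18 degrees of freedom and noncentrality d√(n/2).
- At d = 0.5 the noncentrality is 0.5 × √5 = 1.118. The central 95% of observed d is about -0.40 to 1.52.
- Conversely, a pilot that observed exactly d = 0.5 would have a 95% confidence interval of -0.40 to 1.38.
- Reaching p<0.05 needs an observed d above 2.101 × √(2/10) = 0.94. Power is 10%, 19% and 40% at d = 0.3, 0.5 and 0.8. If the true d is 0.5, significant results favouring active average about d = 1.24.

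**3. Feeding the pilot d into a sample size.** Per arm, n ≈ 2(1.960 + 0.842)²/d² = 15.70/d². At d = 0.5 this is 62.8, so 63, or 64 with the t distribution. In simulated pilots with true d = 0.5, the quartiles of observed d are about 0.199 and 0.828. The formula turns these into 15.70/0.199² ≈ 396 and 15.70/0.828² ≈ 23 per arm.

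A planner would not size a trial on an effect near zero, so the next figures separate pilots with observed d of 0.1 or less:
- about 18% of pilots fall there when the true d is 0.5;
- among the rest, the middle half of planned sizes is about 21 to 112 per arm, against about 64 needed. This range depends on the exclusion: over all pilots the upper quartile is about 390;
- among the rest, the share planning a trial with real power below 50% depends on the assumed effect:

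| Assumed true d | Real power under 50% |
|---|---|
| 0.3 | about 58% |
| 0.5 | about 39% |
| 0.8 | about 27% |

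These figures take 10 evaluable subjects per arm. The 22% to 25% dropout cited in section 17 would leave 7.5 to 7.8 per arm if it applied to the assessments. The effect detectable with 80% power then rises from d = 1.32 to 1.51 (8 per arm) or 1.63 (7 per arm).

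**4. Multiplicity.** Comparisons: 5 × 3 = 15. This count is derived, not stated. It leaves out the Fisher tests for adverse events (section 16) and the CAST domain scores.
- Independent tests: 1 − 0.95^15 = 53.7%; expected false positives 15 × 0.05 = 0.75.
- Equal correlation among the test statistics: about 36% at 0.5 and 26% at 0.7.
- Sparse relapse: six of the 15 tests use C-SSRS data (two outcomes, three visits). With 10 per arm and assumed relapse rates of 10% and 20%, an uncorrected chi-square test has a true error of about 0.9% and 3.0%, and a t-test on zero-heavy scores behaves similarly. Even under independence the total falls to 1 − 0.95^9 × 0.991^6 ≈ 40%, or 1 − 0.95^9 × 0.97^6 ≈ 47.5%. So 54% is a ceiling.

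**The case against.** The plan is more modest than a quick reading suggests. Aim 2 speaks of a preliminary signal, Hypothesis 2 says only that the result will help to set the effect size, the efficacy outcomes are secondary, and 20 was never presented as powered for them. Step 3 models the harshest use, in which the point estimate is the only input. All of that is fair, and later planners could bring in other evidence. But the documents name no other input, and section 17 drops the caution by attaching a significance rule to every comparison.

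A pilot need not control familywise error. That is also right, and no adjustment is asked for here. The difficulty is the verdict of significance, not the lack of a correction.

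Three stronger readings are tempting, and the documents do not support them:
- *An unlucky pilot would end the programme.* There is no efficacy stop/go rule. The stated thresholds concern feasibility and acceptability.
- *The tests are unplanned.* The outcomes, visits and test types are all listed in advance. They are unadjusted and unranked, which is a different criticism.
- *Fifteen results will be called significant.* The label applies only where the threshold is met.

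The remedy is not free of noise either. A pooled SD on 18 degrees of freedom has a 95% interval of about 0.76 to 1.48 times its estimate, and a sham relapse count of 2/10 would have an exact interval of 3% to 56%. This stands, and the fix allows for it.

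**Conclusion.** The point holds as a matter of wording and interpretation. A C-SSRS contrast from about 10 per arm is too imprecise to set the effect size for a full trial. At an assumed true d of 0.5, about two in five of the pilots encouraging enough to be used (observed d above 0.1) would lead to a trial with less than even odds of detecting that effect. The proportion runs from about 58% to 27% as the assumed d goes from 0.3 to 0.8.

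The 15 planned comparisons carry a chance of at least one false positive of up to 54%, roughly 26% to 36% at correlations of 0.7 to 0.5, and less if relapse is rare. These figures rest on the assumed effects and correlations and on normally distributed scores. Because C-SSRS intensity starts near its floor, a standardized difference on it may be less stable than the normal model implies.

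Nothing here affects the primary feasibility criterion, the conduct of the study or subject safety.

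**What to change.** 1. **Hypothesis 2.** State that the full trial will be sized on a smallest worthwhile difference fixed in advance. Let the pilot inform the SD, the sham relapse rate and attrition, each quoted with its confidence interval and read alongside external data.
2. **Section 17, main efficacy comparison.** Name the C-SSRS intensity difference at the day-14 [+7] assessment as the one Hypothesis 2 comparison, reported with a 95% confidence interval. Say explicitly that this visit represents the end of treatment. Section 4 labels day 14 post-treatment, but the feasibility window is three weeks from receipt of the device, so some subjects may still be having sessions.
3. **Section 17, everything else.** Report the other outcomes and visits as exploratory estimates with confidence intervals, and remove the significance rule for them.

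The cost is wording only; no assessment, visit or subject is added. The pilot gives up its claim to supply an effect size and to declare significance on secondary outcomes.

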2. BACKGROUND AND RATIONALE

Suicide is one of the main causes of mortality worldwide, and its rates have increased in the US (1-3). There is no single cause of suicide and suicidal behavior, rather it is the result of a complex interaction between social, environmental, and individual risk factors (4). Approximately 90% of those who died by suicide had a psychiatric disorder, mainly a mood disorder (5), which allows for a small narrowing of intervention selection insofar as components of evidence-based treatments for mood disorders may be helpful for SI and behavior. Indeed, SI (i.e., thoughts about death or wanting to be dead) is present in approximately 20% of individuals with mood disorders and is an independent risk factor for a suicide attempt (6, 7).

Neuroimaging studies demonstrate an association between SI and alterations in neural circuits, including increased functional connectivity in the default mode network (DMN) (8-12). The DMN is a large-scale brain circuit that shows activity when the brain is at rest and not engaged in goal-directed activities (13). The DMN is related to self-oriented patterns of thought, which include rumination and introspective states, and comprise medial, lateral, and inferior parietal cortices, medial prefrontal cortex (mPFC), and precuneus/posterior cingulate cortex (PCC) (13, 14). Chase et al. (2017) have tested if individuals with SI would present different patterns of connectivity within the DMN compared with healthy controls. Indeed, participants with SI evince altered functional connectivity in the cingulate cortex and between ventral and

dorsal posterior cingulate cortex (PCC) and dorsal anterior cingulate cortex (ACC) (10). Taylor et al. (2015) have investigated whether suicidal thoughts are associated with gray matter volumetric and white matter microstructural differences comparing depressed participants with or without SI and healthy controls. These investigators found that alterations in parietal white matter microstructure observed in depressed individuals with SI compared to those without SI are potentially related to the DMN's posterior hub (8). Interestingly, studies with ketamine, an intervention that rapidly reduces SI (15), showed decreased functional connectivity in the DMN (16-18). Transcranial direct-current stimulation (tDCS), a non-invasive, non-pharmacologic neurostimulation intervention that has demonstrated efficacy for the treatment of mood disorders (19-21), has also been associated with alteration of cerebral connectivity in the DMN; for instance, reducing synchrony in DMN components (22, 23), and hence may prove to be a useful adjunct in treating SI.

In a randomized controlled trial (RCT), Brunoni et al. (2013) evaluated the efficacy and safety of tDCS and sertraline, compared to each treatment in isolation, in patients with major depressive disorder (MDD) and found that tDCS was significantly superior to placebo on the Montgomery-Asberg Depression Rating Scale (MADRS) scores (21). A systematic review and meta-analysis for tDCS in treating bipolar depression also noted significant findings for reducing depressive symptoms, even after controlling for sample sizes. In addition, results suggested that effects could be achieved within one week of treatment (24). tDCS twice a week was also associated with low relapse rates in a 6-month follow-up with individuals who had responded to the treatment (25).

The mechanism of action of tDCS is still unknown. However, as mentioned above, some studies show an association between tDCS and modulation of brain connectivity in the DMN (22, 23), a neural network associated with several psychiatric disorders and maladaptive behaviors, including SI (26-29). Pena-Gomez et al. (2012) have investigated whether the activity of the "anticorrelated network" (AN), brain regions that have a negative correlation with DMN, would predominate over DMN with tDCS over the dorsolateral prefrontal cortex (DLPFC). These authors found a reduction in synchrony within DMN components and increased synchrony within its AN (23). The influence of tDCS in resting-state networks was also tested by Keeser et al. (2011), who showed that, compared with sham tDCS, active tDCS induced changes in the functional connectivity of the DMN (22).

Prior history of suicide attempt is the main risk factor for suicide behavior. Nanayakkara et al. (2013) used public data to investigate risk factors for adolescent suicide and found that prior-year suicide attempt was the greatest risk factor for re-attempt, even controlling for current or past depression (30). Data from a 5-year study of individuals who have attempted suicide show that almost 40% of participants made at least one suicide attempt during the study period. In this same study, 6.7% of the 302 participants died by suicide during the 5-year follow-up (31). In a retrospective-prospective cohort study with 1,490 participants who attempted self-harm, Bostwick et al. (2016) reported 81 (5.4%) deaths by suicide during the study follow-up, representing 62.3% of the total deaths in the period (32).

Luxton et al. (2013) have investigated suicide rates among U.S. military service members after a psychiatric hospitalization and reported an almost 5-fold higher suicide rate in this population compared to the general population of active-duty U.S. military personnel. In addition, the highest suicide rate was in the first 30 days after hospitalization, 8.2 times higher than the risk one-year post hospitalization. In this study, almost one-third of those who died by suicide had an episodic mood disorder (33). Another study showed a suicide rate of 263.9

suicides per 100,000 person-years soon after hospital discharge among U.S. Army soldiers, almost 14-fold higher compared with the total U.S. Army. Previous suicidal behavior was one of the main predictors (OR=2.9) (34). Forte el al. (2019) addressed suicidal risk after hospital discharge in a review paper that included 48 studies with a total of 1,700,785 participants followed for almost 8 years after a psychiatric hospitalization (35). The authors noted that about 20% of the suicides and attempts had occurred within 15 days following hospital discharge and more than a quarter in the first month. The results also showed that mood disorders were associated with the highest risk (35).

These studies clearly show that evidence-based interventions for suicidal behavior prevention offered soon after psychiatric inpatient hospitalization are of major significance, especially for high-risk groups such as individuals with a history of SI and behavior and mood disorders. However, the low rate of outpatient treatment engagement and the high rate of dropout from an outpatient service after discharge from an emergency department is a challenge (36), and speaks to the need to overcome these barriers to care. Effective tDCS stimulation requires daily sessions, typically performed in an outpatient clinic. For some patients, this presents a serious barrier. Specifically, for patients in the first weeks after discharge, residual symptoms, and the need to reorganize personal issues and obligations after a period at the hospital may prevent them from commuting to daily visits at health facilities to complete a non-invasive brain stimulation treatment. Thus, to address low treatment engagement and overcome barriers to care with this population, this study will test the feasibility of a home-based tDCS protocol for preventing SI relapse soon after hospitalization discharge.

Home-based tDCS has proven feasible in treating pain in older adults with knee osteoarthritis. In a study by Ahn et al. (2019), participants provided average ratings of 9.57, 9.67, and 9.8 out of a possible 10 concerning 1) preparation of the device, 2) ease of use of the device, and 3) confidence in the use of home-based tDCS, respectively. In addition, no participants reported adverse effects with the treatment (37). Alonzo et al. (2019) tested the efficacy, tolerability, and feasibility of home-based tDCS for treating depression in an open-label trial monitored remotely. The authors found that the intervention was associated with a significant decrease in depressive symptoms, with minor and transient side effects, and excellent adherence (38). The tolerability and safety of home-based tDCS were assessed over 6,779 sessions from six clinical trials, with daily session, varying from 10 to 60 applications. The authors reported no serious adverse events, a similar proportion of tingling (68%), itching (41%), and warmth sensation (42%) between active and sham groups, and no participant discontinuation due to lack of tolerability (39).

Taken together, previous studies provide evidence that: 1) SI is an independent risk factor associated with suicide attempts; 2) SI has been associated with hyperactivity in the DMN brain circuit, which is related to rumination and self-oriented patterns of thought; 3) tDCS, a safe, non-invasive type of neurostimulation, seems to decrease the synchrony within DMN. To our knowledge, no study has investigated tDCS as an adjunctive intervention for SI or behavior. Considering the safety and ethical concerns about any research that deals with SI and behavior as the primary outcome, best practices treatment must be offered; therefore, we intend to investigate tDCS as an adjunctive treatment for the prevention of SI relapse after discharge from a psychiatric emergency or inpatient unit of which they were admitted with SI or attempt.

